## Appendix C: Modified Whole Body Itch Numeric Rating Scale (NRS)

Instruction: Please think about **your whole body (including your scalp)** when answering the question below.

Please rate the itching severity due to your psoriasis by circling the number that best describes your worst level of itching in the past 24 hours.

0      1      2      3      4      5      6      7      8      9      10

0 = No itching

10 = Worst itch imaginable

Naegeli, 2015.

## Appendix D: Scalp Itch Numeric Rating Scale (NRS)

Please rate the itching severity of your **scalp** due to your psoriasis by circling the number that best describes your **worst** level of itching in the **past 24 hours**.

CCI

CELGENE PROPRIETARY INFORMATION

CCI

CELGENE PROPRIETARY INFORMATION

## Appendix F: The Dermatology Life Quality Index (DLQI)

The aim of this questionnaire is to measure how much your skin problem has affected your life OVER THE LAST WEEK. Please check one box for each question.

|   |  |
|---|--|
| 1. Over the last week, how itchy, sore, painful or stinging has your skin been?  |  Very much  A lot
 A little  Not at all                                       |
| 2. Over the last week, how embarrassed or self conscious have you been because of your skin?                                 |  Very much  A lot
 A little  Not at all                                       |
| 3. Over the last week, how much has your skin interfered with you going shopping or looking after your home or yard ? |  Very much  A lot
 A little  Not at all  Not relevant |
| 4. Over the last week, how much has your skin influenced the clothes you wear?   |  Very much  A lot
 A little  Not at all  Not relevant |
| 5. Over the last week, how much has your skin affected any social or leisure activities?                              |  Very much  A lot
 A little  Not at all  Not relevant |
| 6. Over the last week, how much has your skin made it difficult for you to do any sport ?                                    |  Very much  A lot
 A little  Not at all  Not relevant |
| 7. Over the last week, has your skin prevented you from working or studying ?   |  Yes  No  Not relevant   |
| If "No", over the last week how much has your skin been a problem at work or studying ?                               |  A lot  A little  Not at all   |

## Appendix F: Dermatology Life Quality Index (DLQI) (Continued)

|  |  |
|--|--|
| 8. Over the last week, how much has your skin created problems with your partner or any of your close friends or relatives ?        | _ Very much _ A lot _
A little _ Not at all _
_ Not relevant |
| 9. Over the last week, how much has your skin caused any sexual difficulties ?  | _ Very much _ A lot _
A little _ Not at all _
_ Not relevant |
| 10. Over the last week, how much of a problem has the treatment for your skin been, for example, by making your home messy, or by taking up time? | _ Very much _ A lot _
A little _ Not at all _
_ Not relevant |

Finlay, 1994.

CELGENE PROPRIETARY INFORMATION

CCI

CELGENE PROPRIETARY INFORMATION

CCI

CELGENE PROPRIETARY INFORMATION

CCI

CELGENE PROPRIETARY INFORMATION

CCI

CELGENE PROPRIETARY INFORMATION

## Appendix K: Treatment Schema for Dose Titration at Baseline

| Dose
Group                      | Day 1   |  | Day 2   |   | Day 3   |   | Day 4                                     |   | Day 5                                     |   | Days 6 -7                              |   |
|------------------------------------|---|--|---|---|---|---|---|---|---|---|--|---|
|                                    | AM  | PM   | AM  | PM  | AM  | PM  | AM  | PM  | AM  | PM  | AM                                     | PM  |
| Placebo
(dummy
titration)    | 10 mg
placebo
+ 20 mg
placebo
+ 30 mg
placebo    | 10 mg
placebo
+ 20 mg
placebo
+ 30 mg
placebo | 10 mg
placebo
+ 20 mg
placebo
+ 30 mg
placebo    | 10 mg
placebo
+ 20 mg
placebo
+ 30 mg
placebo    | 10 mg
placebo
+ 20 mg
placebo
+ 30 mg
placebo    | 10 mg
placebo
+ 20 mg
placebo
+ 30 mg
placebo    | 20 mg
placebo
+ 30 mg
placebo | 20 mg
placebo
+ 30 mg
placebo    |
| 30 mg
apremilast
(titration) | 10 mg
apremilast
+ 20 mg
placebo
+ 30 mg
placebo | 10 mg
placebo
+ 20 mg
placebo
+ 30 mg
placebo | 10 mg
apremilast
+ 20 mg
placebo
+ 30 mg
placebo | 10 mg
apremilast
+ 20 mg
placebo
+ 30 mg
placebo | 10 mg
apremilast
+ 20 mg
placebo
+ 30 mg
placebo | 10 mg
placebo
+ 20 mg
apremilast
+ 30 mg
placebo | 20 mg
placebo
+ 30 mg
apremilast | 20 mg
placebo
+ 30 mg
placebo | 20 mg
placebo
+ 30 mg
apremilast |

## Appendix L: Treatment Schema for Dose Titration at Week 16

| Dose
Group                           | Day 112  |  | Day 113  |  | Day 114  |  | Day 115                          |                                  | Day 116                          |                                  | Days 117 through 118             |                                  |
|---|--|--|--|--|--|--|----------------------------------|----------------------------------|----------------------------------|----------------------------------|----------------------------------|----------------------------------|
|   | AM   | PM   | AM   | PM   | AM   | PM   | AM                               | PM                               | AM                               | PM                               | AM                               | PM                               |
| Placebo to 30 mg apremilast (titration) | 10 mg apremilast + 20 mg placebo + 30 mg placebo | 10 mg placebo + 20 mg placebo + 30 mg placebo    | 10 mg apremilast + 20 mg placebo + 30 mg placebo | 10 mg apremilast + 20 mg placebo + 30 mg placebo | 10 mg apremilast + 20 mg placebo + 30 mg placebo | 10 mg placebo + 20 mg apremilast + 30 mg placebo | 20 mg placebo + 30 mg apremilast | 20 mg placebo + 30 mg apremilast | 20 mg placebo + 30 mg apremilast |
| 30 mg apremilast (dummy titration)      | 10 mg placebo + 20 mg placebo + 30 mg apremilast | 10 mg placebo + 20 mg placebo + 30 mg apremilast | 10 mg placebo + 20 mg placebo + 30 mg apremilast | 10 mg placebo + 20 mg placebo + 30 mg apremilast | 10 mg placebo + 20 mg placebo + 30 mg apremilast | 10 mg placebo + 20 mg placebo + 30 mg apremilast | 20 mg placebo + 30 mg apremilast |

## Appendix M: Titration Blister Card Configuration

### CC-10004-SPSO-001 30mg Titration Card (30 day +3 Extra)

|  |  |    |    |     |     |  |    |     |     |     |  |
|--|--|----|----|-----|-----|--|----|-----|-----|-----|--|
|  |  | 1  | 10 | 20p | 30p |  | 1  | 10p | 20p | 30p |  |
|  |  | 2  | 10 | 20p | 30p |  | 2  | 10  | 20p | 30p |  |
|  |  | 3  | 10 | 20p | 30p |  | 3  | 10p | 20  | 30p |  |
|  |  | 4  |    | 20  | 30p |  | 4  |     | 20p | 30  |  |
|  |  | 5  |    | 20p | 30  |  | 5  |     | 20p | 30  |  |
|  |  | 6  |    | 20p | 30  |  | 6  |     | 20p | 30  |  |
|  |  | 7  |    | 20p | 30  |  | 7  |     | 20p | 30  |  |
|  |  | 8  |    | 20p | 30  |  | 8  |     | 20p | 30  |  |
|  |  | 9  |    | 20p | 30  |  | 9  |     | 20p | 30  |  |
|  |  | 10 |    | 20p | 30  |  | 10 |     | 20p | 30  |  |
|  |  | 11 |    | 20p | 30  |  | 11 |     | 20p | 30  |  |
|  |  | 12 |    | 20p | 30  |  | 12 |     | 20p | 30  |  |
|  |  | 13 |    | 20p | 30  |  | 13 |     | 20p | 30  |  |
|  |  | 14 |    | 20p | 30  |  | 14 |     | 20p | 30  |  |
|  |  | 15 |    | 20p | 30  |  | 15 |     | 20p | 30  |  |
|  |  | 16 |    | 20p | 30  |  | 16 |     | 20p | 30  |  |
|  |  | 17 |    | 20p | 30  |  | 17 |     | 20p | 30  |  |
|  |  | 18 |    | 20p | 30  |  | 18 |     | 20p | 30  |  |
|  |  | 19 |    | 20p | 30  |  | 19 |     | 20p | 30  |  |
|  |  | 20 |    | 20p | 30  |  | 20 |     | 20p | 30  |  |
|  |  | 21 |    | 20p | 30  |  | 21 |     | 20p | 30  |  |
|  |  | 22 |    | 20p | 30  |  | 22 |     | 20p | 30  |  |
|  |  | 23 |    | 20p | 30  |  | 23 |     | 20p | 30  |  |
|  |  | 24 |    | 20p | 30  |  | 24 |     | 20p | 30  |  |
|  |  | 25 |    | 20p | 30  |  | 25 |     | 20p | 30  |  |
|  |  | 26 |    | 20p | 30  |  | 26 |     | 20p | 30  |  |
|  |  | 27 |    | 20p | 30  |  | 27 |     | 20p | 30  |  |
|  |  | 28 |    | 20p | 30  |  | 28 |     | 20p | 30  |  |
|  |  | 29 |    | 20p | 30  |  | 29 |     | 20p | 30  |  |
|  |  | 30 |    | 20p | 30  |  | 30 |     | 20p | 30  |  |
|  |  | 31 |    | 20p | 30  |  | 31 |     | 20p | 30  |  |
|  |  | 32 |    | 20p | 30  |  | 32 |     | 20p | 30  |  |
|  |  | 33 |    | 20p | 30  |  | 33 |     | 20p | 30  |  |

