## 7. DESCRIPTION OF STUDY TREATMENTS

### 7.1. Description of Investigational Product(s)

The chemical name of apremilast (CC-10004) is acetamide, N-[2-[(1S)-1-(3-ethoxy-4-methoxyphenyl)-2-(methylsulfonyl)ethyl]-2,3-dihydro-1,3-dioxo-1H-isoindol-4-yl].

Apremilast will be supplied by the Sponsor, Celgene Corporation, and labeled appropriately as investigational product for this study.

All IP will be provided in blister cards throughout the entire study. Apremilast will be provided as 10, 20, or 30 mg tablets. Placebo will be provided as identically appearing 10, 20, or 30 mg tablets. Apremilast, the investigational product (IP), will be taken orally twice daily, approximately 12 hours apart, without restriction of food or drink. To mitigate potential gastrointestinal (GI) side effects, dose titration will be implemented in the first week of this study (see [Table 4](#)).

During Week 0 (Days 1-7), subjects will be dispensed dose titration blister cards with 10, 20, and 30 mg apremilast tablets or identically appearing placebo tablets. The blister cards will contain all IP required for 4 weeks of treatment, with the first 7 days containing the titration supplies or matching placebo (see [Table 4](#) Treatment Schema for Dose Titration at Visit 2 [Week 0] which details the titration supplies from Day 1 to Day 7).

At Visit 2 (Week 0), subjects who meet entry criteria will be randomized using a permuted block randomization in parallel 2:1 to receive either apremilast 30 mg BID or placebo, using a centralized Interactive Response Technology (IRT). IP will be dispensed as indicated below.

- Weeks 0 to 16: Double-blind, Placebo-controlled Treatment Phase: Apremilast 30 mg BID or placebo BID.
  - Week 0 to 1: subjects will be dose titrated as described above and detailed in [Table 4](#).
- Weeks 16 to 32: Apremilast Extension Phase: Apremilast 30 mg BID.
  - Week 16 to 17: subjects will be dose titrated as described below and detailed in [Table 5](#).

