**Table 4: Treatment Schema for Dose Titration at Visit 2 (Week 0)**

|                             | Week 0                     |                            |                            |                            |                            |                            |                  |                  |                  |                  |                  |                  |
|-----------------------------|----------------------------|----------------------------|----------------------------|----------------------------|----------------------------|----------------------------|------------------|------------------|------------------|------------------|------------------|------------------|
|                             | Day 1                      |                            | Day 2                      |                            | Day 3                      |                            | Day 4            |                  | Day 5            |                  | Day 6-7          |                  |
|                             | AM                         | PM                         | AM                         | PM                         | AM                         | PM                         | AM               | PM               | AM               | PM               | AM               | PM               |
| Apremilast 30 mg BID | 10mg A
20mg P
30mg P | 10mg P
20mg P
30mg P | 10mg A
20mg P
30mg P | 10mg A
20mg P
30mg P | 10mg A
20mg P
30mg P | 10mg P
20mg A
30mg P | 20mg A
30mg P | 20mg A
30mg P | 20mg A
30mg P | 20mg P
30mg A | 20mg P
30mg A | 20mg P
30mg A |
| Placebo              | 10mg P
20mg P
30mg P | 20mg P
30mg P |

A=Apremilast; BID= twice daily; P= Placebo.

During Weeks 16 to 32, the IP will remain blinded, to prevent study personnel and subjects from knowing the IP assignment in the Placebo-controlled Treatment Phase and to maintain the blind regarding the initial treatment assignment, all subjects will receive dose titration cards at Visit 7 (Week 16). Although only subjects initially randomized to placebo will be dose titrated during their first week of the Apremilast Extension Phase, all subjects entering the Apremilast Extension Phase will receive identically-appearing titration/treatment cards as shown in [Table 5](#).

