## 7.2. Treatment Administration and Schedule

Investigational product will be taken orally twice daily, approximately 12 hours apart, without restriction of food or drink. To mitigate potential gastrointestinal (GI) side effects, dose titration will be implemented in this study. During Week 1 (Days 1-7) and Week 16 (when placebo subjects are switched to receive apremilast 30 mg BID), subjects will be dispensed blister cards with 10, 20, and 30 mg apremilast tablets or identically appearing placebo for the dose titration. At all other visits where IP is dispensed, apremilast will be provided in blister cards as 10, 20, and 30 mg tablets or identically appearing placebo tablets. The treatment schema for dose titration at baseline and Week 16 is shown in [Table 4](#) and [Table 5](#). Blister card configurations are pictured in [Appendix M](#), [Appendix N](#), and [Appendix O](#).

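### Does the Appendix M blister card contradict the titration in Tables 4 and 5 on Days 4 and 5?

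*Protocol*

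**What the plan says.** Protocol Section 7.1 says that the starting blister cards hold four weeks of product, "with the first 7 days containing the titration supplies or matching placebo", and refers to Table 4, "which details the titration supplies from Day 1 to Day 7". In the apremilast row of Table 4, the four cells from Day 4 AM to Day 5 PM read "20mg A 30mg P | 20mg A 30mg P | 20mg A 30mg P | 20mg P 30mg A", where A is active and P is placebo. The placebo-to-apremilast row of Table 5, for the Week 16 switch, has the same four cells.

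Section 7.2 cites both sources for the same titration. It says "The treatment schema for dose titration at baseline and Week 16 is shown in" Tables 4 and 5, and then "Blister card configurations are pictured in" Appendices M, N and O.

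The Appendix M titration card has a left and a right block for each day and no AM/PM heading. Its Day 3 row is "3 | 10 | 20p | 30p | | 3 | 10p | 20 | 30p", its Day 4 row is "4 | | 20 | 30p | | 4 | | 20p | 30" and its Day 5 row is "5 | | 20p | 30 | | 5 | | 20p | 30". A trailing p is read as placebo and a bare number as active.

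**The concern.** The tables and the card are meant to describe one schedule, and no passage mentions a second. Read literally, the tables place the first active 30 mg tablet at Day 5 PM and the card places it at Day 4 PM.

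The protocol gives the purpose of the titration as mitigating gastrointestinal side effects. If the difference were in the signed protocol, it would describe two first-week exposures for every subject starting apremilast, whether at Week 0 or on switching from placebo at Week 16. The documents do not show which card was packed, so the reader could not tell which exposure lay behind the first-week adverse events.

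**Working it through.** There is no stated figure to reproduce. The check is a slot-by-slot comparison.

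**Inputs.** The apremilast row of Table 4 and the placebo-to-apremilast row of Table 5 each have all 12 cells and are identical. Expanding the Day 6-7 columns to two days gives 7 days × 2 doses = 14 slots. The other input is Days 1 to 7 of the Appendix M card.

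**Orientation.** Reading left as AM and right as PM matches every slot on Days 1 to 3 and leaves 2 mismatches in the week. The reverse reading gives 6. Left is therefore taken as AM; the weekly totals do not depend on this.

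**Active mg, AM / PM.**

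| Day | Tables 4 and 5 | Appendix M | Daily total, tables | Daily total, card |
|---|---|---|---|---|
| 1 | 10 / 0 | 10 / 0 | 10 | 10 |
| 2 | 10 / 10 | 10 / 10 | 20 | 20 |
| 3 | 10 / 20 | 10 / 20 | 30 | 30 |
| 4 | 20 / 20 | 20 / 30 | 40 | 50 |
| 5 | 20 / 30 | 30 / 30 | 50 | 60 |
| 6 | 30 / 30 | 30 / 30 | 60 | 60 |
| 7 | 30 / 30 | 30 / 30 | 60 | 60 |

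- Mismatched slots: Day 4 PM and Day 5 AM, so 2 of 14.
- Totals: 10 + 20 + 30 + 40 + 50 + 60 + 60 = 270 mg in the tables; 10 + 20 + 30 + 50 + 60 + 60 + 60 = 290 mg on the card; difference 20 mg.
- Tablet labels on Days 1 to 7: 3 days × 2 × 3 + 4 days × 2 × 2 = 18 + 16 = 34. Four differ: the 20 mg and 30 mg labels in each of the two slots.

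**Could the reading of the PDF produce this?** Three facts bear on it.

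1. *Runs of identical cells were lost nearby.* The placebo row of Table 4 and the apremilast row of Table 5 each keep 2 of 12 cells. In Appendices K and L, Days 1 to 3 keep 24 of 24 cells but Days 4 to 7 keep only 2 + 3 + 3 + 1 = 9 of 24. Only the captions of Appendices N and O survive.
2. *Appendix M contains a very long run of the same kind.* The pattern of 20 mg placebo with active 30 mg fills the left block from Day 5 to Day 33 (29 slots) and the right block from Day 4 to Day 33 (30 slots), 59 in all.
3. *The mismatches sit at the start of that run.* Under the tables it would begin on Day 6 on the left and Day 5 on the right. On the card it begins one row earlier on each side, and those two rows are the two mismatches. A run extended upward by one row would give exactly this result. So would a real drafting difference.

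Appendices K and L cannot break the tie. Their surviving Day 4 to 7 titration cells show no active 20 mg, which matches neither the tables nor the card, and one Appendix K slot has no active tablet at all.

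**Would any analysis change?** The differing slots fall on Days 4 and 5, inside the SAP's first exposure interval of up to 1 week (Section 11.1.2). SAP Section 9.1 measures exposure as duration. Section 9.2 measures compliance in tablets, and both versions have 34 tablets in the first seven days. The Week 16 endpoint does not refer to the titration.

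**The case for a change.** The strongest case for the concern is that it compares content that is present. The Appendix M grid looks intact: 33 days × 2 sides = 66 slots, all filled, with 18 + 120 = 138 tablets and the expected number per slot (three on Days 1 to 3, two afterwards). Left and right differ on Days 1, 3 and 4, so one side was not simply copied to the other. A single misread character cannot explain four changed labels. The matter concerns first-week dosing, and the check costs almost nothing.

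The comparison stands, and so does the exclusion of a single-character error. A full grid, however, shows only that every slot was filled, not that each was filled correctly; a repeated pattern started one row early also leaves a complete grid. Ruling out the single-character slip leaves the more plausible mechanism open. What survives is a reason to look at the original image once.

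**Conclusion.** An error in the plan is not established. In the text available, the card and the tables differ in 2 of 14 slots, 270 against 290 mg over seven days. The difference has the form that a misread run of identical rows would take, in a part of the document where such runs were repeatedly damaged. Tables 4 and 5 agree cell for cell in their titration rows, and Sections 7.1 and 7.2 name them as the schema; Appendix M is cited only as a picture of the card. Product comes in pre-packed cards, so no site or subject has to choose between the passages, and no effect on subjects, on the Week 16 endpoint or on any planned adverse-event table has been shown.

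This is at most a minor verification query: compare Appendix M with the original image and the packaged card specification. If the same two slots differ there, Appendix M and Tables 4 and 5 must be reconciled as an administrative correction, with no change to any analysis. No view is taken on which schedule is right.

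The conclusion rests on reading left as AM and a trailing p as placebo, both supported by Days 1 to 3. It also rests on the artefact remaining a live possibility, which only the original image can settle.

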## Appendix N: Active Treatment Blister Card Configuration

CC-10004-SPSO-001 30mg Treatment Card (30 day +3 Extra)

## Appendix O: Placebo Treatment Blister Card Configuration

CC-10004-SPSO-001 Placebo Treatment Card (30 day +3 Extra)

## 1. JUSTIFICATION FOR AMENDMENT

Changes included in this amendment are summarized below:

- Modified Section 4.2 Inclusion Criteria 9 such that approved contraceptive options includes 2 options to reflect the standard contraception language for all Apremilast studies.
- In Section 6.4 Efficacy Assessment: added instructional text to Scalp Physician Global Assessment to guide investigators on method of assessment.
- Provided clarification to Section 6.5 Safety Assessment that subjects with positive TB testing at screening who have documentation of completed TB treatment will qualify for the study. This is in line with the Exclusion Criteria 8.
- Modified Sections 9.2, 9.5, 11.1 and 11.2 by changing protocol violations to protocol deviations to reflect current sponsor standards.
- Modified Section 8.2 Prohibited Concomitant Medications and Procedures: Topical therapy. Replaced acetylsalicylic acid with salicylic acid preparations. This is in line with Exclusion Criteria 17.
- Provided updates to the following appendices to reflect the validated and IRB approved questionnaires that were provided to the subjects since the initiation of the study:
  - Appendix C: Modified Whole Body Itch Numeric Rating Scale;
  - Appendix D: Scalp Itch Numeric Rating Scale;
  - Appendix F: The Dermatology Life Quality Index;

CC-10004-SPSO-001  
Apremilast  
Summary of Changes

1. LIST OF ABBREVIATIONS

Table 1: Abbreviations and Specialist Terms

AE	Adverse Event
ANCOVA	Analysis of Covariance (model)
ATC	Anatomical-Therapeutic-Chemical
BID	Twice Daily
BMI	Body Mass Index
CCI	[REDACTED]
CI	Confidence Interval
CMH	Cochran-Mantel-Haenszel
CRF or eCRF	(electronic) Case Report Form
CRO	Contract Research Organization
CRP	Clinical Research Physician
DLQI	Dermatology Life Quality Index
FCBP	Female of Childbearing Potential
CCI	[REDACTED]
[REDACTED]	[REDACTED]
HRQoL	Health-Related Quality of Life
IP	Investigational Product
IRT	Interactive Response Technology
ITT	Intent-to-Treat
IVRS	Interactive Voice Response System
LOCF	Last Observation Carried Forward
LS Mean	Least Square Mean
CCI	[REDACTED]
MedDRA	Medical Dictionary for Regulatory Activities
MI	Multiple Imputation
NRI	Non-responder Imputation

NRS	Numeric Rating Scale
CCI	[REDACTED]
CCI	[REDACTED]
PP	Per-Protocol (population)
PRO	Patient Reported Outcome
PT	Preferred Term
SAE	Serious Adverse Event
SAP	Statistical Analysis Plan
ScPGA	Scalp Physician Global Assessment
SD or STDEV	Standard Deviation
SE	Standard Error
SI	Standard International (unit)
CCI	[REDACTED]
SOC	System Organ Class
CCI	[REDACTED]
TEAE	Treatment-emergent Adverse Event
CCI	[REDACTED]
US	United States
WHODD	World Health Organization Drug Dictionary

2. INTRODUCTION

This statistical analysis plan (SAP) describes the analyses and data presentations for Celgene's protocol CC-10004-SPSO-001, "A Phase 3, Multi-Center, Randomized, Placebo-Controlled, Double-Blind Study of the Efficacy and Safety of Apremilast (CC-10004) in Subjects with Moderate to Severe Plaque Psoriasis of the Scalp".

An interim analysis is not planned. After all subjects have completed the Week 16 Visit (or discontinued from the study), a Week 16 data restriction will be performed, the primary data analysis will be conducted **CCI** [REDACTED]. However, unblinded data will only be made available to select Sponsor and Contract Research Organization (CRO) team members involved with analysis of the data **CCI** [REDACTED] **CCI** [REDACTED]. All other Sponsor, site, and CRO personnel directly involved with the conduct of the study, will remain blinded to treatment assignments until the final database lock at the conclusion of the study. At the end of the study, after all subjects have completed, or have been discontinued from the Apremilast Extension Phase (Weeks 16 to 32) and the Observational Follow-up Phase, the final data base lock and analysis will be performed and a final Clinical Study Report will be generated.

CCI
[REDACTED]

This SAP provides a more technical and detailed elaboration of the statistical analyses as outlined and/or specified in the study protocol final version dated 29 Mar 2017 and final version of Amendment 1 dated 30 Nov 2017. The SAP will be finalized and signed prior to the unblinding of the Week 16 database. All statistical analyses detailed in this SAP will be the responsibility of the Biostatistics & Programming department of **CCI** [REDACTED] and will be conducted using SAS® Version 9.3 or higher.

